8.8 Adverse Event Severity Classification

Severity will be defined according to the following CTCAEv.4 criteria:

Grade 1	Mild; asymptomatic or mild symptoms; clinical or diagnostic observations only; intervention not indicated.
Grade 2	Moderate; minimal, local or noninvasive intervention indicated; limiting age-appropriate instrumental ADL.
Grade 3	Severe or medically significant but not immediately life-threatening; hospitalization or prolongation of hospitalization indicated; disabling; limiting self care ADL**
Grade 4	Life-threatening consequences; urgent intervention indicated.
Grade 5	Death related to AE

8.9 Adverse Event Relationship Classification

Relationship to study product administration will be determined as follows:

- *No Relationship*: No relationship between the AE and the administration of study treatment and a known relationship to other etiologies such as concomitant medications, surgical procedure, or subject's clinical state.
- *Possible Relationship*: An AE that follows a reasonable temporal sequence from administration of the study treatment and follows a known response pattern to the study treatment but could have been produced by the participant's clinical state or by other therapies.
- *Probable Relationship*: An AE that follows a reasonable temporal sequence from administration of the study treatment; follows a known response pattern to the study treatment; and cannot be reasonably explained by the known characteristics of the participant's clinical state or by other therapies.
- *Definite Relationship*: An AE that follows a plausible temporal sequence from administration of the study treatment and follows a known response pattern to the study treatment. The reaction cannot be reasonably explained by the known characteristics of the subject's clinical state or other modes of therapy administered to the subject.
- *Unknown/Impossible to Determine*: Given the information available, sequence and timing of events, it is unknown or impossible to determine the relationship of the AE with the study treatment.

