6.6.2 Adverse Events & Complications

Tables to summarize the incidence rates will be created for each of the following groups:

- Adverse events
- Serious adverse events
- Adverse events leading to premature discontinuation
- Adverse device effects (ADE)
- Serious adverse device effects (SADE)
- Unanticipated serious adverse device effects (USADE)
- Adverse events by intensity
- Adverse events by relationship to study product administration

Adverse events that led to premature discontinuation from the study will be listed. Serious adverse events, SADE and USADE will also be listed.

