8.4 Adverse Device Effect (ADE)

An Adverse Device Effect is an adverse event related to the use of a medical device.

This definition includes adverse events resulting from insufficient or inadequate instructions for use, deployment, installation, or operation, or any malfunction of the medical device.

This definition includes any event resulting from use error or from intentional misuse of the medical device.

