8.6 Unanticipated Serious Adverse Device Effect (USADE)

An Unanticipated Serious Adverse Device Effect is a serious adverse device effect which by its nature, incidence, severity, or outcome has not been identified in the current version of the risk analysis report.

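### Section 8.9 makes a known response pattern a condition of every related category, so an event of a genuinely new kind may be rated Unknown and miss the device-effect labels and the resection reporting rule

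*Protocol*

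**What the plan says.** Protocol section 8.9 introduces its five-category scale with "Relationship to study product administration will be determined as follows". The three categories that express a relationship share one element:

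- *Possible*: "An AE that follows a reasonable temporal sequence from administration of the study treatment and follows a known response pattern to the study treatment but" might instead be due to the patient's condition or another treatment.
- *Probable*: the event "follows a known response pattern to the study treatment; and cannot be reasonably explained by the known characteristics of the participant's clinical state", nor by other therapies.
- *Definite*: "An AE that follows a plausible temporal sequence from administration of the study treatment and follows a known response pattern to the study treatment", again with no reasonable alternative explanation.

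The other two are *No Relationship*, which requires a known link to some other cause, and *Unknown/Impossible to Determine*.

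The device-effect definitions are nested. Under section 8.4, "An Adverse Device Effect is an adverse event related to the use of a medical device", and the section expressly includes events arising from inadequate instructions, malfunction, use error or misuse. A SADE (8.5) is an ADE with a serious outcome. A USADE (8.6) is a SADE "which by its nature, incidence, severity, or outcome has not been identified in the current version of the risk analysis report".

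Section 6.6.2 plans incidence tables for ADEs, SADEs and USADEs and a table by relationship, and it lists SAEs, SADEs and USADEs individually. The SAP repeats the definitions and offers no other causality scale. Its section 7.10 summarises events related to the procedure or device.

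**The concern.** The nature limb of section 8.6 exists to catch a serious device effect of a kind nobody had foreseen. Such an effect is the least likely to follow a known response pattern, yet section 8.9 requires that pattern before any relationship can be recorded. A site that applies the scale as written could therefore withhold a related rating from the type of event the USADE category is meant to bring forward.

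The rating also has consequences beyond the table by relationship. Section 8.11 uses the three related categories as the filter for what is reported during resection. It also extends follow-up beyond the first post-operative visit only for events the investigator judges related. Section 8.12 brings non-serious events to the sponsor within 24 hours when they are ADEs. An event left at Unknown falls outside each of these provisions unless another rule picks it up.

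**Working it through.** No arithmetic applies, and the plan states no figure to reproduce. The check sets the definitions side by side and follows one event through them.

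**Test event.** An adverse event with reasonable timing after ablation, of a kind not previously known for microwave ablation, with no other known cause, and not due to malfunction, inadequate instructions, use error or misuse.

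| Category in 8.9 | Condition that decides the case | Met? |
|---|---|---|
| No Relationship | known link to another cause | No |
| Possible | known response pattern | No |
| Probable | known response pattern | No |
| Definite | known response pattern | No |
| Unknown/Impossible to Determine | relationship cannot be determined | Only category left |

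The known-pattern condition appears in 3 of 3 related categories, each time as a required element and not as one factor to weigh. The test event fails 4 of 5 categories.

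**From rating to label.** A USADE must be a SADE (8.6), a SADE must be an ADE (8.5), and an ADE must be related to use of the device (8.4). Section 8.9 is the only rule in either document for deciding relationship, and nothing says how an Unknown rating is treated when ADE, SADE or USADE status is assigned. The test event may therefore receive none of the three labels.

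**From rating to reporting.**

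- *During ablation*: section 8.11 records every event whatever its relationship, so the test event is captured.
- *During resection*: section 8.11 undertakes to report only events rated in the three related categories. The test event is not among them.
- *If serious, at any time*: section 8.12 brings it to the sponsor within 24 hours, section 8.1 sends it to post-market vigilance whatever the cause, and section 6.6.2 lists it as an SAE. It is captured, but possibly without the device-effect label.
- *If non-serious and arising at resection*: neither 8.12 nor the SAE listing picks it up. Section 8.2 and SAP section 7.10 speak more broadly of collecting adverse events in all enrolled subjects, so the outcome depends on which passage a site follows.

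**Events that are not blocked.** An event of a known kind that is unexpected only in incidence, severity or outcome can be rated related and can become a USADE. So can one arising from malfunction, inadequate instructions, use error or misuse, because section 8.4 admits these without any pattern requirement.

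**Probable against Definite.** Both require a known pattern and the absence of a reasonable alternative explanation. The only difference is whether the timing is called reasonable or plausible, and neither word is defined as the stricter.

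**The case against.** A reader might infer that no effect new in nature can ever become a USADE, so that the USADE count for such effects is zero by construction. The documents do not support that, for three reasons.

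- The known response pattern in 8.9 is undefined and is not tied to the risk analysis report against which 8.6 judges an effect. An effect known for microwave ablation generally but absent from that report could be rated related and still be a USADE by nature. Lists of this sort do differ: pleural effusion and acute respiratory distress (7.2) and allergic or toxic reaction (8.7) are not named in the hazard list of 7.1. The report itself is not available, so which events would qualify cannot be settled.
- Section 8.4 is an independent route for malfunction, inadequate instructions, use error and misuse.
- No passage says that the 8.9 rating decides USADE status. Section 8.4 does not refer to 8.9, and 6.6.2 tabulates relationship separately from the device-effect groups. An assessor could classify an event as an ADE directly.

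It can also be said that little is hidden. Serious events are reported and listed individually in a study of at most 30 subjects, and the table by relationship would show Unknown ratings. An independent medical monitor adjudicates pre-specified events under a charter that is not available. All of this stands, and it limits the harm.

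It does not remove the conflict. An assessor who reaches USADE for the test event must set the scale in 8.9 aside, and sites may differ in doing so. An unforeseen kind of event would not naturally be on a pre-specified list. The SAE safeguards do not reach non-serious events at resection, where 8.11 does use the rating as a filter.

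**Conclusion.** The concern holds for a narrow but safety-relevant class: events of a kind not previously known for microwave ablation, with no other known cause, and not covered by the specific inclusions in 8.4. For these, a literal reading of 8.9 leaves only Unknown. The consequences are possible misclassification, a possible under-count in the ADE, SADE and USADE tables, and possible loss of non-serious new events arising at resection.

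The conclusion rests on two assumptions: that sites apply 8.9 as written, and that the 8.9 rating is what they use to decide whether an event is related in the sense of 8.4. The second is a natural inference but is not stated. The documents give no basis for estimating how many events would be affected, and the number may well be none. Because serious events remain visible, this is a worthwhile wording correction and not a failure of SAE reporting. The primary and secondary endpoints are untouched. The overlap of Probable and Definite is a side issue, since both count as related and only one descriptive table separates them.

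**What to change.** Reconcile 8.9 with 8.4 to 8.6 and with 8.11:

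1. In 8.9, make a known response pattern a feature that supports a related rating and not a condition of it.
2. State that events rated Unknown are reported under 8.11 and, if serious, are carried to the SADE/USADE assessment.
3. Optionally, combine Probable and Definite for tabulation.

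It may be tempting to redefine Possible as any event for which the device or ablation cannot be excluded as a cause. Section 8.2 concedes that surgical and ablation effects will sometimes be impossible to separate, particularly after surgery, so that test could move many post-resection events into Possible. Routing Unknown-rated events to assessment is more contained.

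The cost is a wording amendment and matching guidance for completing the adverse event form. Somewhat more events will be counted as possibly device- or ablation-related, mainly after surgery, and the report should say so when it presents those tables.

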8.10 Adverse Event Outcome Classification

Outcome of the event will be defined according to the following:

- *Resolved*: The event has fully resolved at the end of the study.
- *Resolved with sequelae*: The event has resolved, but retained pathological conditions resulting from the prior disease or injury.
- *Continuing*: The event is ongoing at the end of the study.
- *Death*: This event is determined to be the cause of death.

8.11 Adverse Event Recording and Reporting

[figure not shown]
In addition to the adverse event reporting required for post market device reporting, adverse events occurring during the ablation procedure and/or attributed to the ablation procedure will be recorded in an AE CRF and reported in clinical study reports.

Assessment of the occurrence of an AE will be based on changes in the subject's physical examination, laboratory results and/or signs and symptoms. Adverse events will be monitored until conclusion of the first post-operative follow-up visit unless the Investigator determines the event is related to the device or ablation procedure, in which case they will be monitored until resolution if possible. Medical care will be provided, as defined in the informed consent, for any device or ablation procedure related AEduring study participation. Adverse events will be collected on an AE eCRF and applicable source documentation. To the extent possible, the event to be recorded and reported is the event diagnosis as opposed to event symptoms (e.g., fever, chills, nausea and vomiting in the presence of a clinically diagnosed infection is to be reported as infection only). For the purposes of this protocol, only those AEs occurring after initial administration of anesthesia will be recorded.

The following should not be considered an AE:

- A condition requiring a preplanned procedure unless the condition worsened since screening
- A preexisting condition found as a result of screening, unless the condition has worsened since the screening visit, and is noted on the day of the procedure

All AEs observed during the ablation procedure for this study, regardless of severity or relationship to the device will be recorded on the appropriate CRF and reported in clinical study reports. Only device and/or ablation procedure related AE's deemed possible, probable, or definitely related will be reported during the surgical resection. To ensure reported events can be attributed to the device and/or ablation procedure, it is strongly recommended that a safety evaluation be performed immediate post-ablation procedure to capture acute events and again prior to the scheduled surgical resection.

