SAE	Serious adverse event; an adverse event that 
 a) led to death, b) led to serious deterioration in the health of the subject, that either resulted in 
 1) a life-threatening illness or injury, or 2) a permanent impairment of a body structure or a body function, or 3) in-patient or prolonged hospitalization, or 4) medical or surgical intervention to prevent life-threatening illness or injury or permanent impairment to a body structure or a body function, c) led to fetal distress, fetal death or a congenital abnormality or birth defect 
NOTE: Planned hospitalization for a pre-existing condition, or a procedure required by the clinical investigational plan, without serious deterioration in health, is not considered a serious adverse event.

TEAE	Treatment-emergent adverse event; any event not present prior to the initiation of the treatments or any event already present that worsens in either intensity or frequency following exposure to the treatments.
USADE	Unanticipated serious adverse device effect; serious adverse device effect which by its nature, incidence, severity or outcome has not been identified in the current version of the risk analysis report.

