5.7.6 Planned Surgical Resection

Surgical resection and postoperative management will occur per standard local practice. The entirety of each target tumor and the microwave ablation zone should be resected. Every attempt will be made by each site to perform the surgical resection immediately after or the same day of the ablation procedure. However, if an unforeseen event occurs resulting in an OR scheduling conflict, surgical resection performed up to 36 hours after the ablation procedure is acceptable.

However, surgical resection of the ablation zone performed beyond 36 hours will be considered a protocol deviation.

The following procedural variables will be collected:

- Device and/or ablation procedure related adverse events as defined in section 6.6.2.

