5.7.7 Postoperative Evaluation / End of Study Visit

The study subject will complete the study at the conclusion of the first post-operative visit, conducted per standard local practice, but occurring no later than 30 days after the scheduled resection.

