8.2 Adverse Event (AE)

An Adverse Event is any untoward medical occurrence, unintended disease or injury, or untoward clinical signs (including abnormal laboratory findings) in subjects, users or other persons, whether or not related to the medical device.

Adverse events will be collected starting from the initial administration of anesthesia to the patient until conclusion of the first post-operative follow-up visit. All enrolled subjects will be evaluated for Adverse Events regardless of whether or not the subject received the planned ablation and resection.

It should be noted the risks identified above are similar to those noted for standard lung resection. In some cases, it will be impossible to differentiate surgery induced AE's from ablation induced AEs, specifically for AE's that occur after surgery. This should be noted as a limitation in quantifying device and/or ablation procedure related AEs .

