**Confidential**

### **7.10. Safety Evaluation**

Adverse events for all enrolled subjects will be collected and reported. All reported adverse events will be presented based on the ITT population and tabulated by system organ class and preferred term. The incidence of peri-procedural and post-procedural events related to the actual procedure or the study device will be summarized and reported using counts, and percentages.

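### Protocol 8.11, as ordinarily read, stops counting the worsening of a screening-found condition as an adverse event if it is first noted after the procedure day, contradicting 8.2

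*Protocol*

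**What the plan says.** Protocol section 8.11 introduces a two-item list with "The following should not be considered an AE".

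- The first item is "A condition requiring a preplanned procedure unless the condition worsened since screening". Its exception has no day limit.
- The second item is a preexisting condition found through screening, with the exception "unless the condition has worsened since the screening visit, and is noted on the day of the procedure".

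Section 8.2 sets the collection period: "Adverse events will be collected starting from the initial administration of anesthesia to the patient until conclusion of the first post-operative follow-up visit". Section 5.7.7 places that visit as "occurring no later than 30 days after the scheduled resection", and section 5.7.6 says that "surgical resection performed up to 36 hours after the ablation procedure is acceptable".

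Section 8.11 also limits the AE form to events that occur during the ablation or are attributed to it. SAP section 7.10 states "Adverse events for all enrolled subjects will be collected and reported" and tabulates the reported events in the ITT population.

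**The concern.** The second bullet's exception has two parts joined by 'and': the condition has worsened, and it is noted on the procedure day. A condition that was stable on the procedure day and deteriorates some days later meets only the first part. It stays on the list of things that are not AEs, although the subject is still within the period in which section 8.2 collects AEs.

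The study delivers thermal injury to the lung in people with lung tumors. Section 5.5.2 excludes only GOLD Stage IV emphysema, so less advanced emphysema can be present at entry. Later deterioration of such a condition, judged related to the ablation, is a harm that the safety summary should show. The bullet acts at the site, when the form is completed. The SAP tabulates only what was reported, so no later analysis can bring the event back.

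**Working it through.** The plan gives no figure to reproduce here. The check compares the rules and then does two small pieces of arithmetic.

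**1. Logic of the bullet.** Rule: not an AE unless (worsened since screening) and (noted on the procedure day).

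| Screening-found condition | Worsened? | Noted on procedure day? | AE under the 8.11 bullet? | Inside the 8.2 period? |
|---|---|---|---|---|
| Worsens on the procedure day, after anesthesia starts | yes | yes | yes | yes |
| Worsens later, before the first post-operative visit | yes | no | no | yes |

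The second row is the contradiction. Under the neighboring bullet on preplanned procedures, the same later worsening would leave the list, because that exception asks only for worsening since screening.

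**2. Length of the period.** Inputs: resection up to 36 hours after ablation (5.7.6) and a final visit up to 30 days after the scheduled resection (5.7.7).

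36/24 + 30 = 1.5 + 30 = 31.5 days at most.

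The exception names one day of that period. This describes the calendar. It is not a fraction of events lost, because events need not be spread evenly. The day itself is also not firmly defined: the assessments table in 5.7.1 allows for more than one procedure day.

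**3. Whether another rule restores the event.** Sections 8.1 and 8.12 require reporting of serious adverse events and adverse device effects. Sections 8.3 and 8.4 define both as kinds of adverse event. An occurrence ruled not to be an AE does not clearly qualify as either, so these sections do not reliably bring it back.

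**4. What the attribution rule leaves.** Later worsening not attributed to the ablation is outside the AE form under 8.11 in any case. The bullet therefore matters mainly for later worsening that is attributed to the device or ablation.

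**5. Size per subject.** Input: up to 30 subjects (protocol 5.5, SAP section 6).

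1/30 = 0.033, or about 3.3 percentage points of AE incidence for each affected subject who has no other AE. With fewer than 30 subjects it is more. A subject who already has another AE adds nothing to overall incidence, although the event would still be missing from its own system organ class and preferred term row.

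**The case against.** The strongest reply concerns grammar. The 'unless' clause is set off by commas. Taken as a parenthesis, the bullet says that a condition found at screening and noted again on the procedure day is not an AE unless it has worsened. Under that reading later worsening is not excluded and the bullet agrees with 8.2. This may have been the intent. The reading is more awkward, but it is available. What stands is that the text does not compel the exclusion. The problem remains, because the two readings give opposite recording instructions to as many as 10 sites, and neither document says which applies.

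Several stronger inferences are tempting and are not supported:

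- **That all later worsening is lost because of this bullet.** The attribution limit in 8.11 already removes much of it, and section 8.2 concedes that events after surgery often cannot be separated from surgical effects. New events such as pneumothorax or bleeding are not preexisting conditions and are untouched. A condition already known from the medical history is arguably not one found as a result of screening.
- **That a number of lost events can be stated.** The documents give neither the frequency of screening-found conditions nor the rate at which they worsen. Any count would rest on invented rates.
- **That the treatment-emergent definition is breached in the analysis.** Section 2.0 does include "any event already present that worsens in either intensity or frequency following exposure to the treatments", with no day limit. But the term appears only in the two definition lists. No collection rule or safety table uses it, so it shows at most what the authors regarded as an event.
- **That failing to record worsening before anesthesia is a further defect.** It follows from the stated start of AE collection.

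**Conclusion.** Wrong as written, in a limited form. On its ordinary reading the second bullet of 8.11 contradicts both section 8.2 and the bullet before it, because it denies AE status to worsening first noted after the procedure day. The alternative reading turns this into inconsistent recording between sites; it does not make the text safe.

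The practical loss is mainly later worsening of a screening-found condition that would be attributed to the device or ablation. The number of such events cannot be estimated from the documents. Each affected subject with no other AE moves overall incidence by about 3.3 points, assuming the full 30 subjects are enrolled and analyzed.

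The conclusion rests on sites applying the bullet literally. It does not assume that any event has been missed.

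**What to change.** Reconcile the bullet with 8.2 by removing the day limit. For example: *a preexisting condition identified at screening, unless it becomes worse at any point between the start of anesthesia and the end of the first post-operative visit.*

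Carry the same wording into the instructions for completing the AE form. Leave the attribution rule in 8.11 unchanged. The SAP needs no change, since it tabulates whatever is reported.

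The cost is one amended sentence and slightly more events to record. No visit or test is added.
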